6.3.3 Variables

The following variables will be collected for each AE:

- AE (verbatim)
- The date when the AE started and stopped
- The maximum CTCAE grade reported
- Changes in CTCAE grade (report only the maximum CTCAE grade for a calendar day)
- Whether the AE is serious or not
- Investigator causality rating against the IPs (yes or no)
- Action taken with regard to IPs
- Administration of treatment for the AE
- Outcome

In addition, the following variables will be collected for SAEs:

- Date the AE met criteria for SAE
- Date the Investigator became aware of the SAE
- Seriousness criteria
- Date of hospitalization
- Date of discharge
- Probable cause of death
- Date of death
- Whether an autopsy was performed
- Causality assessment in relation to study procedure(s)
- Causality assessment in relation to other medication, as explained in Section 6.3.4
- Description of the SAE

The grading scales found in the revised NCI CTCAE version 4.03 will be utilized for all events with an assigned CTCAE grading. For those events without assigned CTCAE grades, the recommendation in the CTCAE criteria that converts mild, moderate, and severe events into CTCAE grades should be used. A copy of the CTCAE version 4.03 can be downloaded from the Cancer Therapy Evaluation Program website (http://ctep.cancer.gov).

It is important to distinguish between serious and severe AEs. Severity is a measure of intensity whereas seriousness is defined by the criteria in Section 6.2 and the Additional Safety Information in APPENDIX A. An AE of severe intensity need not necessarily be considered serious. For example, nausea that persists for several hours may be considered severe nausea, but not a SAE unless it meets the criteria shown in Section 6.2 and APPENDIX A. On the other hand, a stroke that results in only a limited degree of disability may be considered a mild stroke but would be a SAE when it satisfies the criteria shown in Section 6.2 and APPENDIX A.

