3.1.1 Adverse Events (AEs)

AEs and SAEs will be collected throughout the study, from time of signature of informed consent and up to 90 days after the last dose of immunotherapy agents (ie, the last dose of durvalumab or tremelimumab). MedDRA (using the latest or current MedDRA version) will be used to code the AEs. AEs will be graded according to the National Cancer Institute (NCI) Common Terminology Criteria for AEs (CTCAE Version 4.03).

A treatment emergent adverse event (TEAE) is an AE with an onset date or a pre-existing AE worsening following the first dose of study treatment through to 90 days after the last dose of immunotherapy agents. For the durvalumab + tremelimumab modules, in the event of the components being administered separately, then date of first dose/last dose will be considered as the earliest/latest dosing date of either component. Any AE occurring before study treatment (i.e. before the administration of the first dose on Study Day 1) will be included in the AE listings, but will not be included in the summary tables (unless otherwise stated). These will be referred to as 'pre-treatment'. However, any AE occurring before the administration of the first dose on Study Day 1 that increases in severity after the first dose will be regarded as treatment emergent and thus will be included in the majority of summary tables.

For patient level summaries, if more than one AE is coded to the same PT for the same patient, the patient will be counted only once in summaries using the most serious grading on causal relationship to study treatment.

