- PDL1: high >=25% vs low <25%. If data is available from the central laboratory, the central laboratory result will be used in the group derivation, otherwise, the local test result will be used.

Subgroup analyses will also be conducted for the summary of OS, ORR and DCR in the following subgroups of the SS:

- Age at baseline: <65 vs 65-74 vs ≥ 75 years of age
- ECOG performance status at baseline: 0-1 vs 2
- Primary tumor location: Bladder vs Renal pelvis and Ureter vs Urethra vs Other
- Stage: III vs IV
- Tumor histology: Urothelial (i.e. TCC) vs non-urothelial
- Previous platinum chemotherapy: platinum vs non-platinum chemotherapy
- Best response to previous therapy (CR vs PR vs SD vs PD)

- Baseline metastases: liver (+/- other visceral or non-visceral metastases) vs lymph node metastases only
- PDL1: high \geq 25% vs low \leq 25%

No formal comparisons will be performed between the subgroups.

Time-to-event analyses

Time-to-event of AESI and imAE:

Time-to-onset of AESI/imAE (by AESI/imAE category) and time-to-intervention with steroids, immunosuppressants and/or hormone replacement therapy to treat an AESI/imAE will be defined as time from first dose of durvalumab +/- tremelimumab to first onset of the event.

Time-to-event (TTE) is defined in months as follows:

TTE (months) = (Date of event or censoring–Date first dose of durvalumab [durvalumab + tremelimumab for the combinations modules]+1)/(365.25/12)

Time-to-resolution (TTR) of an AESI/imAE type is defined as the time from the first onset of an AESI/imAE type to the resolution of the AESI/imAE type. TTR is defined in months as follows:

TTR (months) = (Date of AESI/imAE resolution or censoring–Date of AESI/imAE onset+1)/(365.25/12)

Analysis of TTR will only include patients who have experienced an AESI/imAE.

The distribution of TTE and TTR times will be estimated using the Kaplan-Meier method (Kaplan and Meier 1958) and summarised using the median, twenty-fifth and seventy-fifth percentiles. TTE and TTR of imAE of NCI CTCAE grade >=3 will also be produced.

Deaths

A summary of deaths will present number (n) and percentage (%) of patients for the following categories:

- Total number of deaths (including deaths occurring within 90 days after last dose of study medication and deaths occurring after the 90 days post dosing window)

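### Time to onset and time to resolution run from first onset, with no rule for AEs that begin before dosing and worsen afterwards (negative times result) and no stated onset date for grade 3 or higher imAEs

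*SAP*

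**What the plan says.** SAP 4.2.1 (Time-to-event analyses) states that time to onset, by AESI/imAE category, "will be defined as time from first dose of durvalumab +/- tremelimumab to first onset of the event". The formula is "TTE (months) = (Date of event or censoring–Date first dose of durvalumab" plus one day, divided by 365.25/12. Time to resolution "is defined as the time from the first onset of an AESI/imAE type to the resolution of the AESI/imAE type". Both are to be estimated by Kaplan-Meier and summarised by the median and quartiles. For severe events the only text is "TTE and TTR of imAE of NCI CTCAE grade >=3 will also be produced".

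SAP 3.1.1 defines a treatment-emergent AE as one that "is an AE with an onset date or a pre-existing AE worsening following the first dose of study treatment". It adds that an AE occurring before the first dose "that increases in severity after the first dose will be regarded as treatment emergent and thus will be included in the majority of summary tables". SAP 4.2.1 bases most AE summaries on treatment-emergent AEs unless it says otherwise, and its AESI and imAE tables are explicitly treatment emergent. The time-to-event text names no other set.

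The AE event rate per 100 patient-years, also in SAP 4.2.1, ends each affected patient's time at risk at the date of first onset or the last day of study medication, whichever is earlier.

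Protocol 6.3.3 collects, for each AE, its start and stop dates and "Changes in CTCAE grade (report only the maximum CTCAE grade for a calendar day").

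**The concern.** The rule that decides which AEs count and the rule that dates them do not match. SAP 3.1.1 lets an AE in either because its onset is post-dose or because it worsened post-dose. SAP 4.2.1 dates every AE from onset. An AE admitted because it worsened is therefore dated at a point before any drug was given.

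The result is an impossible time for an event that the SAP itself counts. The programmer must drop it, set it to zero or re-date it, and the SAP does not say which. If it is dropped, the onset analysis no longer agrees with the incidence table.

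The grade 3 or higher analysis has a related gap. It should show when severe immune-mediated toxicity appears and how long it lasts, but the SAP does not say which date starts a severe event that began at a lower grade. Characterising the severity and outcome of AESIs is the study's primary objective, and SAP 4.1 says the descriptive data may support health authority considerations. The dates should be fixed in advance.

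**Working it through.** The plan gives no figure to reproduce, so its own formulas are applied to assumed dates. Days are counted from first dose, with the dosing day as day 0, and one month is 365.25/12 = 30.4375 days.

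**Can pre-dose start dates occur?** Yes. AEs are collected from consent (Protocol 6.3.1), and screening runs from Day -28 to Day -1 (Protocol 4.1).

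**Does another rule move them?** Only for partial dates. SAP 3.1.3 sets a partial start date to the first treatment date if it could fall on that date. Its example is a start in June 2017 with the day unknown and first dose on 21 June 2017. That AE is dated 21 June and gets (0 + 1)/30.4375 = 0.03 months. With the same first dose, a complete start date of 11 June is left alone and gets (-10 + 1)/30.4375 = -0.30 months. The less complete record gets the valid time.

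**Time to onset, (start day + 1)/30.4375, for an AE that later worsens:**

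| AE start (day) | Time to onset (months) |
|---|---|
| -28 | -27/30.4375 = -0.89 |
| -14 | -13/30.4375 = -0.43 |
| -7 | -6/30.4375 = -0.20 |
| -2 | -1/30.4375 = -0.03 |
| -1 | 0/30.4375 = 0.00 |
| 0 | 1/30.4375 = 0.03 |

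The time is negative for a start two or more days before dosing, and zero for a start one day before.

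**Case A, pre-dose AE (assumed dates).** It starts on day -14, worsens on day 20 and resolves on day 50.
- From first onset: time to onset -13/30.4375 = -0.43 months; time to resolution (50 + 14 + 1)/30.4375 = 2.14 months.
- From worsening: time to onset 21/30.4375 = 0.69 months; time to resolution (50 - 20 + 1)/30.4375 = 1.02 months.
- The excess in time to resolution is the 34 days from first onset to worsening: 34/30.4375 = 1.12 months.
- Event-rate denominator: by plain subtraction of dates, this patient contributes -14 days of time at risk.

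**Case B, severe imAE (assumed dates).** Grade 1 on day 20, grade 3 on day 62, resolved on day 90.
- From first onset at any grade: time to onset 21/30.4375 = 0.69 months; time to resolution (90 - 20 + 1)/30.4375 = 2.33 months.
- From the grade 3 date: time to onset 63/30.4375 = 2.07 months; time to resolution (90 - 62 + 1)/30.4375 = 0.95 months.
- The two readings differ by 42 days, or 1.38 months, in each measure.

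In general, each day between first onset and escalation makes onset 0.033 months earlier and resolution 0.033 months longer. A gap of 7 days gives 0.23 months, and 28 days gives 0.92.

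**The case against.** **The negative-time case is narrow.** This stands. Protocol 5.2.2 treats worsening of a pre-existing condition as an AE in its own right, so the problem falls mainly on AEs that arise between consent and first dose. Exclusions for autoimmune disease, recent immunosuppression and unresolved grade 2 or higher toxicity reduce it further. An imAE must also be associated with drug exposure, which fits poorly with a pre-dose start. But the SAP applies the same date rule to AESIs, which carry no such requirement.

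**A sensible programmer would use the worsening date.** Perhaps, but SAP 3.1.1 names onset and worsening as alternatives, so first onset does not naturally mean worsening.

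**The grade 3 part reads silence as a rule.** A reader might infer that the SAP dates severe imAEs from their milder phase. It does not say so. The event can equally be read as the grade 3 event, dated when grade 3 is reached. Only the ambiguity is established.

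**Total duration from AE onset is a legitimate measure for an imAE that reached grade 3.** This is accepted. The SAP only needs to say which start date it uses.

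**A rule may exist elsewhere.** The imAE charter in SAP Appendix 1 was not available for this review, so a dating rule there cannot be excluded. SAP 3.1.1.1 cites the charter for identifying imAEs, not for dating them.

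**Conclusion.** The concern holds for AEs that start before dosing and worsen afterwards. On the SAP's text they are counted as treatment emergent, and a complete start date two or more days before dosing gives a negative time to onset (-0.89 months at Day -28). Their time to resolution is too long by the interval from onset to worsening, and they contribute negative person-time to the event rate. For grade 3 or higher imAEs the finding is an unspecified onset date. If the general definition is carried over, severe events look earlier and longer.

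The effect on the reported results cannot be sized. The documents do not say how many AEs begin between consent and first dose and then worsen, or how often and how fast imAEs escalate. A reader might want to state a shift in the reported median in days, but the documents do not support one. The formula allows for censoring and only time to resolution is restricted to patients with an event, so time to onset most naturally covers all treated patients. For uncommon events the Kaplan-Meier quartiles may never be reached.

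No hypothesis is tested, and the primary outcome, AESI incidence, is unaffected. This is a small correction, worth making before database lock because a stated rule yields impossible values.

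**What to change.** In SAP 4.2.1, define the event date for time to onset as:
- for an AE present before first dose, the first post-dose date on which its grade exceeds the pre-dose grade;
- for the grade 3 or higher analysis, the first date the imAE is recorded at grade 3 or higher;
- otherwise, the AE start date.

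For AEs present before first dose, use the same worsening date as the start of time to resolution and as the end of time at risk in the event-rate denominator. State which start date the grade 3 or higher time to resolution uses. If the imAE charter already contains a dating rule, cite it and make the two agree.

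The cost is a short SAP paragraph and one derived date. Protocol 6.3.3 already collects grade changes, at most one grade per calendar day, and SAP 4.2.1 already plans a listing of grade fluctuations for the most severe AEs. No new data are needed.

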 - If year and month are present and day is missing, impute day as last day of the month.
 - When the patient has died in the same month/year of partial stop date, use date of death.
- For medications, a conservative approach will be followed and events will be assumed to be concomitant unless the end date is before the first dose of IP. If the start and end dates are both missing it is considered concomitant.
- In addition for AEs if, for a partial start date, the AE start date could (when also considering the AE end date) potentially be on the first study treatment date, the AE start date will be imputed with the first study treatment date to assume a "worst case" scenario; e.g. AE from UNK-Jun-2017 to 23-Jul-2017 with the first study treatment date 21-Jun-2017, then the AE start date will be imputed to 21-Jun-2017.

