- At least one treatment-emergent serious AESI
- At least one treatment-emergent AESI by maximum NCI CTCAE grade
- At least one treatment-emergent AESI causally related to study medication
- At least one treatment-emergent AESI with fatal outcome
- At least one treatment-emergent AESI which required additional treatment with steroids, immunosuppressants and hormone replacement therapy
- Laboratory findings, vital signs and other safety parameters associated with AESI will be summarised as part of the AESI outcome measures.

Length of intervention with steroids, immunosuppressants and/or hormone replacement therapy for AESIs will be calculated based on treatment start and stop dates. Total treatment

times will then be combined for each patient and summarised for patients experiencing at least one treatment-emergent AESI.

The exact 95% CIs around the incidence estimates will also be reported for each AESI type.

A summary of total duration (days) of AESI will be provided. For ongoing AESI, the date of death or data cut-off will be imputed as end date.

Immuno-mediated adverse events

Summaries of treatment-emergent imAEs by AESI category and PT will include number (n) and percentage (%) of patients who have:

- At least one treatment-emergent imAE
- At least one treatment-emergent imAE by outcome
- At least one treatment-emergent imAE leading to treatment interruption or discontinuation
- At least one treatment-emergent serious imAEs
- At least one treatment-emergent imAE by maximum NCI CTCAE grade
- At least one treatment-emergent imAE causally related to study medication
- At least one treatment-emergent imAE with fatal outcome

Subgroup analyses

Subgroup analyses will be conducted for the summary of TEAEs in the following subgroups of the SS:

- Sex (male versus female)
- Age at baseline: <65 vs 65-74 vs ≥75 years of age). This will be determined from the date of birth (BRTHDAT in the DM domain) and baseline visit (VIS_DAT in the VISIT domain) on the eCRF. Patients with a partial date of birth (ie for those countries where year of birth only is given) will have an assumed date of birth of 1st Jan [given year]). Patients with a missing age value will be included using the mean age and categorised accordingly.
- Race: Asian vs non-Asian
- ECOG performance status at baseline: 0-1 vs 2
- Tumor histology: Urothelial (i.e. TCC) vs non-urothelial

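### Time to resolution of AESIs/imAEs is a Kaplan-Meier estimate with no rule for patients who die unresolved; on the natural reading its quartiles are biased early

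*SAP*

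**What the plan says.** The time-to-event part of SAP 4.2.1 says that TTR "is defined as the time from the first onset of an AESI/imAE type to the resolution of the AESI/imAE type". The formula ends at "TTR (months) = (Date of AESI/imAE resolution or censoring", so there are two end states and death is not named. On the population: "Analysis of TTR will only include patients who have experienced an AESI/imAE". No exclusion is stated for fatal events. On the estimator: "The distribution of TTE and TTR times will be estimated using the Kaplan-Meier method", summarised by the median and the 25th and 75th percentiles. Severe events get their own run: "TTE and TTR of imAE of NCI CTCAE grade >=3 will also be produced".

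No censoring rule for TTR is given. Two rules elsewhere in the SAP touch on death. The AESI duration summary in 4.2.1 says "For ongoing AESI, the date of death or data cut-off will be imputed as end date". The rules for partial AE end dates in 3.1.3 say "When the patient has died in the same month/year of partial stop date, use date of death". Neither is tied to TTR. Fatal events appear in a separate count, "At least one treatment-emergent AESI with fatal outcome", with a matching row for imAEs.

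**The concern.** Death makes resolution impossible, and for a fatal AESI it is the worst outcome of the event itself. Kaplan-Meier treats a censored patient as someone who leaves observation with the same future chance of resolving as those still alive and unresolved. A patient who has died has no such chance. If deaths are censored, the TTR curve describes resolution in a population where nobody dies, not the probability that a patient with the event sees it resolve. The run for grade 3 or higher is exposed by construction, because that set includes grade 5.

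Outcome of AESIs is part of the primary objective (Protocol 2.1, SAP 1.1.1), and SAP 4.1 allows the descriptive results to support health authority considerations. A median or upper quartile of TTR is likely to be read as how long these toxicities take to clear.

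**Working it through.** **Figure in the plan.** None. The documents give no TTR result, no resolution rate and no rate of death after onset, so there is nothing to reproduce. Protocol 1.3.3 mentions limited life expectancy and Protocol 3.1 requires at least 12 weeks, but neither gives a death rate.

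**Direction.** Let λ(u) be the hazard of resolution and μ(u) the hazard of death while unresolved, with cumulative hazards Λ and M.

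- Kaplan-Meier with deaths censored targets 1 − KM(t) = ∫₀ᵗ λ(u) exp(−Λ(u)) du.
- The actual probability of resolution by t is CIF(t) = ∫₀ᵗ λ(u) exp(−Λ(u) − M(u)) du.

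Since exp(−M) ≤ 1, 1 − KM(t) ≥ CIF(t) at every t. Kaplan-Meier quartiles are therefore never later than those of the CIF, and are earlier once resolutions follow deaths.

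**Size, under stated assumptions.** Constant hazards; Kaplan-Meier median 2.0 months, so λ = ln 2 / 2 = 0.3466 per month; a share d dies unresolved, so μ = λd/(1 − d). Then CIF(t) = (1 − d)[1 − exp(−(λ+μ)t)]. The q-quantile is −ln(1 − q/(1 − d))/(λ+μ) and exists only if q < 1 − d.

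Example, d = 20%: μ = 0.3466 × 0.25 = 0.0866 and λ+μ = 0.4332. Median = −ln(1 − 0.5/0.8)/0.4332 = 0.981/0.4332 = 2.26 months. 75th percentile = −ln(1 − 0.75/0.8)/0.4332 = 2.773/0.4332 = 6.40 months.

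Kaplan-Meier with deaths censored gives 0.83 / 2.00 / 4.00 months whatever d is. The last column shows the median if the death date were counted as a resolution, ln 2/(λ+μ).

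| Die unresolved | CIF 25th / median / 75th (months) | Median if death counts as resolution |
|---|---|---|
| 5% | 0.84 / 2.05 / 4.27 | 1.90 |
| 10% | 0.85 / 2.11 / 4.65 | 1.80 |
| 20% | 0.86 / 2.26 / 6.40 | 1.60 |
| 30% | 0.89 / 2.53 / not reached | 1.40 |
| 40% | 0.93 / 3.10 / not reached | 1.20 |
| 50% | 1.00 / not reached / not reached | 1.00 |

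All times scale with the assumed median: at d = 20%, a Kaplan-Meier median of 1 or 3 months corresponds to a CIF median of 1.13 or 3.40 months.

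**Check with administrative censoring.** Simulating 200,000 patients with censoring uniform over 6 to 36 months at d = 20% gives Kaplan-Meier quartiles of 0.84 / 2.00 / 4.00 and CIF quartiles of 0.87 / 2.27 / 6.43, in line with the formulas.

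**Other outputs.** The AESI and imAE tables by outcome and with fatal outcome, and the death categories, are counts and do not enter the TTR curve. The cumulative incidence plots in SAP 4.2.1 concern first occurrence, not resolution.

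**The case against.** The strongest reply is that censoring at death is inferred. The SAP gives no TTR censoring rule, and a programmer who kept deaths in the risk set as unresolved up to the data cut-off would remove the bias. That stands as a limit on certainty: a reader might infer that the SAP prescribes censoring at death, and it does not. But no such corrective rule is written. The only death rules nearby set the date of death as an end date; carried into TTR, they would count a death as a resolution and enlarge the bias.

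Second, AE collection generally stops 90 days after the last dose (Protocol 6.3.1), and events unresolved at the last visit are no longer recorded in the CRF (Protocol 6.3.2). Many later deaths would therefore be censored for end of recording under any method. This also stands. Only deaths within the recording period count, and a death hazard applied indefinitely would overstate the effect.

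Third, the outcome, fatal-outcome, duration and death summaries show the deaths, and SAP 4.1 plans no hypothesis test. This limits the harm but leaves the TTR quartiles as they are.

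Several stronger inferences are tempting and not supported:

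- That death with an open AESI is common here: the documents give no rate.
- That the fatal-outcome row and the TTR result contradict each other: they answer different questions.
- That the primary outcome measure is biased: it is the number and proportion of patients with an AESI (SAP 3.1), which TTR does not affect.
- That a large gap in the percentage resolved at a fixed time will be reported: only quartiles are planned.
- That first onset needs the same change: cumulative incidence of first occurrence is already planned.

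**Conclusion.** The point holds as a fault in the choice of estimator together with a missing rule. Under the natural reading, the planned TTR quartiles are never later, and usually earlier, than those of the probability of resolution among all patients with the event. The claim is about that probability, not about the time taken by patients who did resolve.

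The size cannot be computed from the documents. In the illustration the planned median hardly moves if 5 to 10% die unresolved during AE recording (2.00 against 2.05 to 2.11 months) and moves modestly at 20% (2.26). The upper quartile is the sensitive figure: 4.0 against 6.4 months at 20%, and not reached once 25% or more die unresolved. These values rest on constant hazards and an assumed 2-month Kaplan-Meier median; the direction does not. The change should be made, but no test or decision rule depends on it.

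**What to change.** In the time-to-event part of SAP 4.2.1:

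- Estimate TTR by the Aalen-Johansen cumulative incidence of resolution, with death before resolution during the AE recording period, including fatal AESIs/imAEs, as a competing event.
- Censor only at the end of AE recording or at the data cut-off.
- State that a date of death, including one imputed under the duration or partial-date rules, is never a resolution date.
- Take the quartiles from this curve, shown as not reached where they do not exist, and give the number and percentage dying unresolved beside them. Do the same for imAEs of grade 3 or higher.

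Death dates and AE outcomes are already collected (Protocol 5.1 and 6.3.3). The cost is SAP wording and slightly more programming. The stated times to resolution will look less favourable.

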3. PRIMARY AND SECONDARY VARIABLES

3.1 Safety

The primary outcome measure for the study is the number and proportion of patients with AESI. Pre-defined Medical Dictionary for Regulatory Activities (MedDRA) preferred terms groupings will be used to identify AESI.

'On treatment' will be defined as assessments between date of first dose and 90 days following last dose inclusive.

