- Death related to disease under investigation ONLY, as determined by investigator (including deaths occurring within 90 days after last dose of study medication and deaths occurring after the 90 days post dosing window)
- TEAEs with outcome of death ONLY
- AEs with outcome of death ONLY and onset date falling after 90 days follow-up period
- Deaths related to disease under investigation, as determined by the investigator, and with TEAE with outcome of death
- Deaths related to disease under investigation, as determined by the investigator, and with AE with outcome of death and onset date falling after 90 days follow-up period
- Deaths that occurred 90 days after last dose, and unrelated to AE (ie no AE with outcome of death) or disease under investigation

- Patients with unknown reason for death
- Other deaths

Summary of long term tolerability

To assess long term tolerability, provided that there are a sufficient number of patients with events to warrant it (\geq 10 events), prevalence plots and cumulative incidence plots will be presented for each AESI category and for any other events considered important after review of the safety data.

A prevalence plot provides information on the extent to which the events may be an ongoing burden to patients. The prevalence at time t after first dose of study treatment is calculated as the number of patients experiencing the event divided by the number of patients receiving study treatment or in safety follow-up at time t; generally, t is categorised by each day after dosing. The prevalence will be plotted over time. Multiple occurrences of the same event are considered for each patient but a patient is only counted in the numerator whilst they are experiencing one of the occurrences of the event. The raw cumulative incidence is the actual probability that a patient will have experienced their first occurrence of the event by a given time point.

Treatment exposure

The following summaries related to study treatment will be produced for the SS:

- Total exposure, actual exposure, and total number of cycles received will be summarised separately for the initial treatment phase and the re-treatment phase. For the modules with combination therapy, those summaries will be carried out once for each drug separately and once for combination separately from monotherapy.

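### The SAP gives no rule for death in its Kaplan-Meier times to AESI/imAE onset and resolution; if deaths are censored, as is usual, resolution looks too early and too complete, and onset of common categories too early.

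*SAP*

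**What the plan says.** The time-to-event part of SAP 4.2.1 says: "The distribution of TTE and TTR times will be estimated using the Kaplan-Meier method". The results are to be "summarised using the median, twenty-fifth and seventy-fifth percentiles". The onset formula runs to the "Date of event or censoring", the resolution formula to the "Date of AESI/imAE resolution or censoring". Neither formula says what triggers censoring or on what date, and neither mentions death. The resolution analysis is confined to affected patients: "Analysis of TTR will only include patients who have experienced an AESI/imAE". Onset carries no such restriction.

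Three other outputs bear on the point.

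- **Primary outcome (SAP 3.1).** "The primary outcome measure for the study is the number and proportion of patients with AESI". SAP 4.2.1 adds exact 95% confidence intervals for each AESI type.
- **Total AESI duration (SAP 4.2.1).** "For ongoing AESI, the date of death or data cut-off will be imputed as end date". This is the only AESI time measure with an explicit rule for death.
- **Long-term tolerability (SAP 4.2.1).** Prevalence and cumulative incidence plots are planned for each AESI category with at least 10 events. The SAP explains: "The raw cumulative incidence is the actual probability that a patient will have experienced their first occurrence of the event" by a given time.

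**The concern.** Patients have advanced cancer, and Protocol 3.1 requires a life expectancy of only 12 weeks, so death before onset or before resolution will be common. A formula with two states leaves only censoring for such a patient. Kaplan-Meier then treats the dead as still able to have the event, or to recover from it, at the same rate as those alive. The percentiles answer what would happen if nobody died.

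Time to resolution is the most exposed. The SAP tabulates AESIs and imAEs with fatal outcome, yet in this analysis a patient killed by the event would count as one who might still have resolved. The outcome tables count resolutions but give no timing, and the cumulative incidence plots cover first occurrence only. No other output gives the timing of resolution free of this problem.

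For onset, the plots offer a partial remedy. They are not explicitly promised for imAEs, nor for imAEs of grade 3 or higher, and their formula is not given. SAP 4.1 says that descriptive safety data may support health authority considerations, so the times may be read outside the study report.

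**Working it through.** **The plan's own figure.** The documents give no numerical onset or resolution time. The nearest planning figure is in SAP 1.3: over 75% probability of at least 10 events at 1% incidence with 1200 patients. The exact binomial tail is P(X ≥ 10 | 1200, 0.01) = 0.759, so it reproduces. It does not depend on the choice made here.

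**Model.** All rates below are assumptions. Take constant hazards: λ for the event of interest and d = ln 2 / (median time to death) for death.

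- Kaplan-Meier with death censored: 1 − exp(−λt).
- Cumulative incidence with death competing: λ/(λ+d) × [1 − exp(−(λ+d)t)], with plateau λ/(λ+d).

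**Resolution.** Let λ = 0.10 per month and median survival after AESI onset be 8 months, so d = 0.693/8 = 0.0866.

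- Kaplan-Meier median: 0.693/0.10 = 6.9 months.
- Share resolved by then: (0.10/0.1866) × [1 − exp(−0.1866 × 6.93)] = 0.536 × (1 − 0.274) = 0.389.
- Share ever resolving: 0.536. Kaplan-Meier tends to 100%, and its 75th percentile is 1.386/0.10 = 13.9 months; with death competing, 75% is never reached.
- With median survival of 6 and 12 months the share resolved at 6.9 months is 36% and 42%: 0.464 × (1 − 0.224) and 0.634 × (1 − 0.335).

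With a Kaplan-Meier median of 3 months instead:

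| Median time to death after onset (months) | Median with death competing (months) | Ever resolved |
|---|---|---|
| 3 | not reached | 50% |
| 6 | 4.0 | 67% |
| 12 | 3.4 | 80% |

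**Onset, common or pooled category.** Choose λ so that 1 − KM at 12 months is 50%: λ = 0.693/12 = 0.0578. The Kaplan-Meier 25th percentile is 0.288/0.0578 = 5.0 months and the median 12 months.

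| Median time to death (months) | 25th percentile with death competing (months) | Median with death competing (months) |
|---|---|---|
| 6 | 8.0 | not reached |
| 9 | 6.5 | not reached |
| 12 | 6.0 | not reached |
| 24 | 5.4 | 16.0 |

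**Onset, moderate category.** With λ = 0.02 and median survival 8 months, the Kaplan-Meier 25th percentile is 0.288/0.02 = 14.4 months, yet only 0.02/0.1066 = 18.8% of patients would ever have the event. At 12 months 1 − KM is 21.3% and the cumulative incidence 13.5%. The SAP does not plan to report that 12-month figure; it shows the gap between the two curves.

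**Onset, rare category.** If 1 − KM is 1% at 12 months, λ = 0.000838 and the Kaplan-Meier 25th percentile is 0.288/0.000838, about 343 months. The protocol synopsis gives the study 4 to 5 years. The quartile would not be reached.

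**The case against.** The strongest reply is that the SAP nowhere says that deaths are censored. That is correct: it is an inference from a two-state formula and from ordinary practice. What is documented is the missing rule, and that is a gap on any reading.

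A reader might go further and infer that the plan overstates how many patients have an AESI. The documents do not support that. Onset percentiles are times, and the resolution analysis includes only patients already affected. The number affected comes from crude counts with exact intervals, which do not depend on Kaplan-Meier. Nor are these times the primary outcome measure; they are descriptive summaries in a single-arm study without hypothesis tests.

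Two further points limit the size. AEs are collected to 90 days after the last dose (SAP 3.1.1), so later deaths do not compete with onset inside that window. The relevant hazard is that of death while under observation, which the documents do not give and which may differ from the hazard implied by overall survival. And a quartile that is not reached cannot mislead about timing, so for onset the problem is confined to common or pooled categories.

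The plots also show that the SAP recognises cumulative incidence for first onset. That leaves resolution, and explicitly imAEs, without an equivalent.

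**Conclusion.** The point holds as a gap in specification with a predictable direction of error, and the SAP should be changed. If deaths are censored, time to resolution comes out too short and resolution too complete; time to onset comes out too short for common or pooled categories; and for rare categories the onset quartiles carry little information. On the assumed rates, 36% to 42% of patients, not half, have resolved at the Kaplan-Meier median of 6.9 months. A 25th percentile of onset of 5.0 months becomes 5.4 to 8.0 months when death competes. These sizes rest on constant hazards and on death rates that the documents do not supply; the direction does not depend on the exact values. The primary AESI proportions, their confidence intervals and the sample size stand as they are.

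**What to change.** In the time-to-event part of SAP 4.2.1:

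1. State the censoring rule. For onset, censor at the end of the 90-day safety window or the data cut-off; for resolution, at the last AE follow-up or the data cut-off.
2. Treat death before onset, and death with the event unresolved, as competing events.
3. Report Aalen-Johansen cumulative incidence with 95% confidence intervals at fixed times, for onset by AESI and imAE category (for example those with at least 10 events) and for resolution. This can replace the Kaplan-Meier quartiles or stand beside them.
4. Label any Kaplan-Meier quartiles that are kept as censoring death.
5. Reconcile the resolution analysis with the total-duration summary, which ends an ongoing AESI at death, and say how the two outputs should be read together.

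The cost is SAP wording and modest programming. Protocol 5.1 already collects dates of death. The downside is less direct comparison with studies that report Kaplan-Meier quartiles; keeping them, labelled, beside the new estimates limits that.
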